5.2.18.1. Skeletal Muscle Biopsy

Skeletal muscle biopsy, which will take approximately 1 hour, will be used to sample muscle cells from the Vastus Lateralis (thigh) muscles. Skeletal muscle biopsy will be done on a subset of participants. After cleaning the skin on the front of the thigh with iodine, a local anesthetic will be injected under the skin to reduce feeling and pain in the area of the biopsy. The doctor or a trained/certified designee will make a small incision in the skin and insert a needle under the skin to remove muscle cells from the thigh. Approximately 600 milligrams of muscle will be removed. After the tissue sample is completed, the skin will be held closed with sterile adhesive strips, an antibiotic ointment will be applied, and the area will be covered. An ACE bandage wrap will be applied securely for 1 hour. After 1 hour, the ACE bandage may be loosened, and then removed after 4 hours.

5.2.18.2. Adipose Tissue Biopsy

Adipose tissue biopsy, which will take approximately 1 hour, will be used to sample fat cells from the abdomen (belly). Adipose tissue biopsy will be done on a subset of participants. After cleaning the skin on the front of your abdomen with iodine, a local anesthetic will be injected under the skin to reduce feeling and pain in the area of the biopsy. The doctor or a trained/certified designee will make a small incision in the skin and insert a needle under the skin to remove fat cells from the abdomen. Approximately 3 grams of adipose tissue will be removed. After the fat sample is completed, the skin will be held closed with sterile adhesive strips, an antibiotic ointment will be applied, and the area will be covered.

5.2.18.3. Tissue Processing and Assays

Muscle and adipose samples will be processed locally at the clinical centers using appropriate methods for archiving that will allow for a variety of future measures. Some lab measurements will be collected on fresh tissue locally at the clinical centers at the time of collection or on frozen samples. Muscle and adipose tissue remaining after local analyses will be de-identified and shipped for storing at the biopsy core laboratory in secure and monitored -80°C or liquid nitrogen freezers. Archived samples that remain after planned assays will be made available to investigators through an ancillary proposal process.

5.2.19. Wearable Sensor Validation Studies

In some circumstances, wearable sensors (e.g., smartwatches, chest straps, smart rings, accelerometers, or other sensors) may be placed on participants during the above-mentioned assessments to obtain simultaneous measures for validation purposes. It is anticipated that this would not substantially increase the time spent in the visit or the test but would allow for collection of simultaneous wearable data during other phenotyping studies (e.g., exercise testing).

5.3. Longitudinal Follow-up

All participants, or their designated contacts, will be contacted using the Eureka app (or by telephone) every 6 months for up to 5 years after enrollment. Vital status, hospitalizations, and any urgent outpatient or emergency department (ED) visits for intravenous diuretics for heart failure exacerbation will be recorded. Participation dates in clinical trials and types of interventions will also be captured. Cause of hospitalizations and deaths will be ascertained by the site investigators and further adjudicated by a central Clinical Events Committee (CEC).

5.3.1. Clinical Events Ascertainment

The CEC will adjudicate all deaths, cardiovascular hospitalizations, HF hospitalizations, and unplanned outpatient/ED visits for intravenous diuretics. CEC adjudication will be done centrally by trained staff according to systematic criteria.

5.3.2. Ambulatory Blood Pressure Monitoring

5.3.3. Ambulatory blood pressure monitoring will be performed in all participants. Participants will receive an upper arm blood pressure monitor to wear for 24 consecutive hours. The device will record blood pressure at 15-minute intervals during the 24-hour monitoring period. After the collection period concludes, the participant will return the blood pressure monitor in a pre-paid, pre-addressed mailer to their local study center.
At-home and Wearable Sensors

Participants may also be asked to use other physiologic consumer-grade wearable or at-home sensors. These may include smartwatches, smart rings, sensor patches (worn on chest), under-mattress monitors, polysomnography devices, or on-demand ECG monitors. These devices are meant to monitor a variety of physiologic parameters such as activity, heart rate and rhythm, temperature, pulse oximetry, sleep, respiratory rate, and ballistocardiography to name a few.

The precise devices will be determined by availability and may be utilized in specific subgroups. All data from these devices will be transmitted to the Data Translation Center either via the HeartShare Eureka app or stored in the device for data download upon return.

6. STATISTICAL CONSIDERATIONS

6.1. Statistical Power Overview

We plan to enroll at least 1000 participants (and up to 2000 participants) in the HeartShare Deep Phenotyping Cohort (75% HFpEF, 25% age- and sex-matched individuals without HFpEF). The power calculations below are based on a sample size of 1000 participants. The power calculations below demonstrate that based on the minimal sample size of 1000 participants, we will have ample power to detect clinically significant differences between individuals with and without HFpEF and, additionally, among HFpEF subgroups.

6.2. Power Considerations

Assumptions: 80% Power, two-sided alpha (0.0005-0.01) accounting for multiplicity. Effect size = standardized mean difference. HFpEF subgroup analysis assumes equally sized subgroups (Table 3b, 4b). Sample size considerations accounting for multivariable modeling (i.e., control for confounders) incorporated an adjustment in sample size upward by a factor of $1/(1-R^2)$ – where R^2 is an estimate of the multiple correlation coefficient of group regressed on all other variables likely to be included in the model (i.e., how much of the variability between groups is explained by the confounding factors) (Table 4a, 4b).

Table 3a. Comparisons between HFpEF and non-HFpEF – no control for confounders

Power	HFpEF N	Control N	Effect Size	Alpha
0.8	750	250	0.316	0.0005
0.8	750	250	0.302	0.001
0.8	750	250	0.250	0.01

Table 3b. Comparisons between subgroups within HFpEF – no control for confounders

Power	HFpEF Total N	Number of Subgroups	Subgroup N*	Effect Size	Alpha
0.8	750	4	187	0.451	0.0005
0.8	750	4	187	0.430	0.001
0.8	750	4	187	0.355	0.01

Table 4a. Comparisons between HFpEF and nonHFpEF – assuming multivariable modeling (controlling for confounders)

Power	HFpEF N	Control N	R-squared	HFpEF N Inflated for Multivariable Modeling	Control N Inflated for Multivariable Modeling	Effect Size	Alpha
0.8	600	200	0.2	750	250	0.353	0.0005
0.8	600	200	0.2	750	250	0.338	0.001
0.8	600	200	0.2	750	250	0.279	0.01
0.8	490	175	0.3	750	250	0.381	0.0005
0.8	490	175	0.3	750	250	0.364	0.001
0.8	490	175	0.3	750	250	0.301	0.01

Table 4b. Comparisons between subgroups within HFpEF – assuming multivariable modeling (controlling for confounders)

Power	Sub-group N	R-squared	HFpEF Total N Inflated for Multivariable modeling	Number of Subgroups	Subgroup N Inflated for Multivariable modeling	Effect Size	Alpha
0.8	150	0.2	750	4	187	0.504	0.0005
0.8	150	0.2	750	4	187	0.482	0.001
0.8	150	0.2	750	4	187	0.397	0.01
0.8	131	0.3	750	4	187	0.540	0.0005
0.8	131	0.3	750	4	187	0.516	0.001
0.8	131	0.3	750	4	187	0.425	0.01

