2. OBJECTIVES

2.1. Specific Aims

- **Overall Aim:** To establish both a HF registry and a HFpEF cohort with deep phenotyping and a biorepository to facilitate mechanistic studies and unbiased discovery approaches to HFpEF.
- **Aim 1:** To identify novel diagnostic, physiologic, imaging, and molecular markers that differentiate individuals with and without HFpEF to characterize the pathophysiology and mechanistic basis of the overall HFpEF syndrome.
- **Aim 2:** To investigate the underlying pathophysiological and biological determinants of previously identified HFpEF subtypes, including, but not limited to: (1) obesity with natriuretic peptide deficient phenotype; (2) cardiometabolic-comorbidity-inflammation phenotype; (3) myocardial-predominant phenotype; (4) left atrial myopathy phenotype; (5) supranormal ejection fraction phenotype; (6) pulmonary vascular disease, right heart failure phenotype; (7) chronotropic incompetence predominant phenotype; and (8) peripheral extraction impairment predominant phenotype.
- **Aim 3:** To identify and enable external validation of novel HFpEF subtypes using unsupervised machine learning of deep phenotyping data, images, and multi-omics, followed by further investigation to determine the underlying pathophysiological and biological determinants of these novel HFpEF subtypes.

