6.3. Overview of Statistical Methods

An overview of the statistical methods for the HeartShare Deep Phenotyping Study are presented here. Full details of the statistical methods are available in the HeartShare Manual of Procedures.

- **Aim 1:** To identify novel diagnostic, physiologic, imaging, and molecular markers that differentiate HFpEF from non-HFpEF. We will use standard methods for evaluating differences between cases (HFpEF) and comparators without HFpEF, including t-tests (or non-parametric equivalent, when indicated) for continuous variables and Chi-squared tests (or Fisher exact tests, when indicated) for categorical variables. We will also use linear, logistic, and Cox regression analyses (as indicated), adjusting for potential confounders including multiple hypothesis testing, to examine for statistically significant differences between cases and comparators.
- **Aim 2:** To investigate the underlying pathophysiological and biological determinants of previously identified HFpEF subtypes. Here we will use standard statistical approaches, comparing the previously identified HFpEF subtype to all other HFpEF patients using approaches similar to Aim 1 above. We will follow-up these analyses by bioinformatics analysis including clustering of multi-omic data to determine whether specific molecules and biological pathways are over-represented in the previously identified HFpEF subgroup vs. other types of HFpEF patients and comparators.

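### Tables 3b and 4b give the power for comparing two of four equal HFpEF subgroups, not for the Aim 2 contrast of one subtype against all other HFpEF patients

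*Protocol*

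**What the plan says.** Protocol Section 6.1 fixes the basis of the power statement: "The power calculations below are based on a sample size of 1000 participants". With the 75% HFpEF share given there, that is 750 HFpEF patients. The section concludes that "we will have ample power to detect clinically significant differences between individuals with and without HFpEF and, additionally, among HFpEF subgroups".

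Section 6.2 sets the terms: "Assumptions: 80% Power, two-sided alpha (0.0005-0.01) accounting for multiplicity", with "Effect size = standardized mean difference", and "HFpEF subgroup analysis assumes equally sized subgroups (Table 3b, 4b"). Table 3b lists four subgroups of 187 with detectable effects of 0.451, 0.430 and 0.355 at alpha 0.0005, 0.001 and 0.01. Table 4b repeats this with effective subgroup sizes of 150 (R-squared 0.2) and 131 (R-squared 0.3). Both tables are titled as comparisons between subgroups within HFpEF.

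Section 6.3 describes the Aim 2 analysis as "comparing the previously identified HFpEF subtype to all other HFpEF patients using approaches similar to Aim 1 above". Section 2.1 lists the subtypes. The list is explicitly open-ended, and its last two numbered entries are "7) chronotropic incompetence predominant phenotype; and (8) peripheral extraction impairment predominant phenotype". The protocol gives no expected share for any subtype and does not say whether the subtypes are mutually exclusive.

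**The concern.** The power tables and the Aim 2 analysis describe different comparisons. The tables set one quarter of the HFpEF group against another quarter. Aim 2 sets one subtype, of whatever size it turns out to be, against everyone else with HFpEF. For a given subtype size the second contrast has a much larger reference group, which helps. But the subtype itself may be much smaller than 187, which hurts. Which of the two dominates depends on the subtype's share, and the tables do not vary that share.

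Tables 3b and 4b are the only support for the subgroup part of the statement in Section 6.1, and Aim 2 is one of three numbered aims. A reader planning work on an uncommon subtype would take from Section 6.1 that a difference of about 0.45 SD is detectable with 80% power, and could read a null result as more informative than it is. A reader interested in a common subtype would underestimate what the cohort can show.

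**Working it through.** **Inputs.** From Sections 6.1 and 6.2: 750 HFpEF patients, 80% power, two-sided alpha of 0.0005, 0.001 or 0.01, and effect expressed as a standardized mean difference (SD = 1). From Section 6.3: subtype versus all other HFpEF patients. The subtype share p is my assumption, shown from 5% to 40%.

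**Formula.** For groups of size n1 and n2, the detectable difference is approximately

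d = (z for 1 − alpha/2 + z for 0.80) × √(1/n1 + 1/n2).

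The results below use the exact two-sided noncentral t version.

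**Step 1: reproduce the protocol's figures.** For 187 vs 187, √(2/187) = 0.1034. At alpha 0.0005 the multiplier is 4.322, so the approximation gives 4.322 × 0.1034 = 0.447; the noncentral t gives 0.451.

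| Groups | Noncentral t, alpha 0.0005 / 0.001 / 0.01 | Protocol |
|---|---|---|
| 187 vs 187 | 0.4507 / 0.4305 / 0.3550 | 0.451 / 0.430 / 0.355 (Table 3b) |
| 150 vs 150 | 0.5042 / 0.4815 / 0.3968 | 0.504 / 0.482 / 0.397 (Table 4b, R-squared 0.2) |
| 131 vs 131 | 0.5404 / 0.5159 / 0.4250 | 0.540 / 0.516 / 0.425 (Table 4b, R-squared 0.3) |

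The arithmetic in the tables is right. The protocol does not use the word pairwise, but the table titles and this agreement show that the comparison is one subgroup against one other of equal size. Since 4 × 187 = 748 of 750, the subgroups are separate and together make up the HFpEF group.

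**Step 2: the Aim 2 contrast.** Put n1 = 750p and n2 = 750(1 − p). For p = 12.5% this is 93.75 vs 656.25, √(1/n1 + 1/n2) = 0.1104, and 4.322 × 0.1104 = 0.477 (noncentral t 0.479). Without adjustment:

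| Subtype share | Detectable d, alpha 0.0005 / 0.001 / 0.01 | Power (%) at the Table 3b effects |
|---|---|---|
| 40% | 0.323 / 0.309 / 0.255 | 99.5 / 99.3 / 98.5 |
| 25% | 0.366 / 0.350 / 0.289 | 96.8 / 96.3 / 94.8 |
| 20% | 0.396 / 0.379 / 0.313 | 92.5 / 92.0 / 90.4 |
| 12.5% | 0.479 / 0.458 / 0.378 | 72.2 / 72.2 / 73.6 |
| 10% | 0.528 / 0.505 / 0.417 | 58.3 / 59.1 / 63.1 |
| 5% | 0.727 / 0.695 / 0.574 | 21.2 / 23.2 / 32.2 |
| *Table 3b as stated* | *0.451 / 0.430 / 0.355* | *80* |

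**Step 3: with confounder adjustment.** Multiply both group sizes by 1 − R-squared. At alpha 0.0005:

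| Share | R-squared 0.2 (Table 4b: 0.504) | R-squared 0.3 (Table 4b: 0.540) |
|---|---|---|
| 40% | 0.362 | 0.387 |
| 25% | 0.410 | 0.438 |
| 20% | 0.443 | 0.474 |
| 12.5% | 0.536 | 0.574 |
| 10% | 0.591 | 0.632 |
| 5% | 0.814 | 0.871 |

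**Step 4: break-even share.** The one-versus-rest contrast matches 187 vs 187 when 1/(750p) + 1/(750(1 − p)) = 2/187, that is 750p(1 − p) = 93.5. This gives p = 0.146, or about 110 of 750 patients. The adjusted versions give the same share to within 0.1 percentage point.

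**The case against.** The equal-size assumption is stated openly, the number and size of the subgroups are printed, and the arithmetic is correct. Aim 3 also looks at differences among identified subtypes, and Tables 3b and 4b fit that comparison if there are four equal clusters. So a reader might infer that the tables are wrong or describe no planned analysis. The documents do not support that; what is missing is a row for Aim 2.

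The direction of the error also depends on shares that the protocol does not give. If subtypes overlap, their shares need not sum to 100%, and several could exceed the break-even. A reader might infer that they do overlap, but the protocol is silent on this, and the point does not need it. Even with eight equal, separate subtypes the shift is moderate: 0.451 to 0.479, about 6%. The severe figures need a 5% subtype.

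Finally, enrolment may reach 2000. With 1500 HFpEF patients, a 12.5% subtype has a detectable difference of 0.338/0.323/0.267, better than Table 3b, and the break-even falls to about 6.7%. This is true, but a 5% subtype would still have only 62.5% power at 0.451 (alpha 0.0005), and Section 6.1 rests its statement on the minimum of 1000.

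These arguments limit the scope and severity. They do not supply the power of the Aim 2 contrast.

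**Conclusion.** The point holds for Aim 2. Tables 3b and 4b do not give the power of the subtype-versus-rest comparison, and do not by themselves support the claim of ample power for it at 1000 participants. At the tabulated effects, power for the planned contrast runs from about 21–32% at a 5% share, through 58–63% at 10% and 72–74% at 12.5%, to 95–97% at 25%. This rests on 750 HFpEF patients, a comparison of means with equal variances, and assumed shares.

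Two stronger readings should be resisted. One is that subgroup power is generally overstated or the cohort too small: above a share of about 14.6% the tables understate Aim 2 power. The other is that 15% marks adequate power. It is only where the two contrasts coincide; the protocol names no clinically significant standardized difference, so nothing makes 0.451 a dividing line.

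This should be fixed, but it is not critical: the study is observational, and Sections 6.1 to 6.3 set no primary hypothesis or success rule that depends on these tables.

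**What to change.** 1. Keep Tables 3b and 4b, and label them as comparisons among four equal subgroups, for example Aim 3 clusters if four are assumed there.
2. Add a table of one-versus-rest detectable effects for Aim 2 by subtype share, from 5% to 40%, unadjusted and with R-squared 0.2 and 0.3, at the three alpha levels already used.
3. Qualify the closing sentence of Section 6.1: for Aim 2 the detectable effect depends on the subtype's share, and at 750 HFpEF patients it exceeds the Table 3b and 4b values when the share is below about 15%.

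The cost is a set of recomputed rows and one sentence. Some stated figures become less favourable. No additional participants and no change to the analysis are needed.

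### Table 4a, R-squared 0.3 rows: 490 HFpEF participants inflate to 700, not the printed 750; with the correct 525 all three effect sizes change, by about 1%

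*Protocol*

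**What the plan says.** Section 6.1 of the protocol bases the power calculations on 1000 participants, 75% with HFpEF and 25% comparators, that is 750 and 250. Section 6.2 sets the terms: "Assumptions: 80% Power, two-sided alpha (0.0005-0.01) accounting for multiplicity", and "Effect size = standardized mean difference". For the comparisons that control for confounders it says that the calculation "incorporated an adjustment in sample size upward by a factor of" 1/(1-R²), where R² is the multiple correlation of group membership with the other covariates.

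Table 4a applies this to HFpEF v non-HFpEF. Its columns run: HFpEF N, control N, R-squared, inflated HFpEF N, inflated control N, effect size, alpha. The three rows for R² = 0.3 are:

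- "490 175 0.3 750 250 0.381 0.0005"
- "490 175 0.3 750 250 0.364 0.001"
- "490 175 0.3 750 250 0.301 0.01"

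**The concern.** The rows break the rule stated directly above them. Dividing 490 by 0.7 does not give 750, while the control number in the same rows does inflate as it should. The two uninflated numbers also stand at 2.8:1 (490/175), although the design and every other row of Tables 3a and 4a are 3:1.

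These rows make up half of the adjusted power statement for HFpEF against comparators, the contrast that Aim 1 addresses and for which section 6.3 plans adjusted regression. If 490 was only a typing slip, three cells need changing. If it was used in the calculation, the three effect sizes are also wrong for the design described.

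**Working it through.** **Inputs**, all from sections 6.1 and 6.2: power 80%; two-sided alpha 0.0005, 0.001 and 0.01; effect in standard deviation units; inflation factor 1/(1-R²); target 750 and 250.

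**Step 1: the inflation rule, N/(1-R²), on every adjusted row.**

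| Table | R² | Uninflated N | Calculation | Printed inflated N |
|---|---|---|---|---|
| 4a, HFpEF | 0.2 | 600 | 600/0.8 = 750 | 750 |
| 4a, control | 0.2 | 200 | 200/0.8 = 250 | 250 |
| 4a, HFpEF | 0.3 | 490 | 490/0.7 = **700** | **750** |
| 4a, control | 0.3 | 175 | 175/0.7 = 250 | 250 |
| 4b, subgroup | 0.2 | 150 | 150/0.8 = 187.5 | 187 |
| 4b, subgroup | 0.3 | 131 | 131/0.7 = 187.1 | 187 |

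Only the 490 fails. The gap is 50 of 750 (6.7%), too large for rounding. Working back, 750 × 0.7 = 525, and 525:175 is 3:1. The other possible reading, that the inflated number should be 700, would make the total 700 + 250 = 950, against the 1000 of section 6.1.

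**Step 2: do the printed effect sizes come from 490?** The detectable difference by the normal approximation is

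d = (z(1-α/2) + z(0.80)) × √(1/n₁ + 1/n₂),

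with z(0.80) = 0.8416 and z(1-α/2) = 3.4808, 3.2905 and 2.5758. The sums are 4.3224, 4.1321 and 3.4174.

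- 490 v 175: √(1/490 + 1/175) = 0.08806, so d = 0.3806, 0.3639, 0.3010. These round to the printed 0.381, 0.364 and 0.301.
- 525 v 175: √(1/525 + 1/175) = 0.08729, so d = 0.3773, 0.3607, 0.2983.

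**Step 3: the same with the noncentral t distribution.**

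| Alpha | Printed | 490 v 175, normal | 490 v 175, t | 525 v 175, normal | 525 v 175, t |
|---|---|---|---|---|---|
| 0.0005 | 0.381 | 0.3806 | 0.3824 | 0.3773 | 0.3789 |
| 0.001 | 0.364 | 0.3639 | 0.3654 | 0.3607 | 0.3621 |
| 0.01 | 0.301 | 0.3010 | 0.3017 | 0.2983 | 0.2990 |

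Neither method gives the printed values from 525 v 175. Of the four combinations, only 490 v 175 by the normal approximation gives all three.

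**Step 4: consequence.** At the printed effect sizes, 525 v 175 has power 0.812, 0.811 and 0.809 by the normal approximation (0.807, 0.806 and 0.806 by t), about one point above the nominal 80%.

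**The case against.** The strongest reply is that nothing depends on these cells. The effect sizes move only in the third decimal, by 0.003 to 0.004 under the normal approximation and 0.002 under t. The table errs on the cautious side. The rows report detectable effects at a fixed enrolment, so no sample size, alpha or analysis follows from them. All of that stands, and it limits the weight of the point. It does not make the rows right.

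A second reply is that the effect sizes are correct for the 490 and 175 printed beside them. That is true under the normal approximation. But the rows claim to describe 750 and 250 after inflation, and for that design they are wrong.

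A third reply concerns method. The protocol names none, and the tables do not follow a single one. Table 3a and most of Table 4a match the normal approximation, while Tables 3b and 4b match noncentral t: for 187 v 187 at alpha 0.0005 the normal value is 0.447, the t value 0.451, and 0.451 is printed. Within Table 4a, 600 v 200 at alpha 0.001 gives 0.3374 by the normal approximation and 0.3385 by t, where 0.338 is printed. So the inference that 490 was used in the calculation is very likely rather than certain. The need to change the effect sizes does not rest on it, because 525 v 175 fits the printed values under neither method.

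**Conclusion.** The point holds. In the three R² = 0.3 rows of Table 4a the uninflated HFpEF number is wrong by 35 (490 for 525), equivalent to 50 after inflation (700 for 750). The three effect sizes beside it do not belong to the 750 v 250 design. They should be about 0.377, 0.361 and 0.298 (normal) or 0.379, 0.362 and 0.299 (noncentral t), against 0.381, 0.364 and 0.301 as printed.

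The size is about 1% or less, and conservative: the table slightly overstates the smallest detectable difference. The 1000-participant basis and the statement that power is sufficient are unaffected. The conclusion rests on two things that the protocol itself states, the 1/(1-R²) rule and the 750/250 split. The exact replacement values also depend on the method, which the protocol does not name.

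**What to change.** In Table 4a, replace 490 by 525 in the three R² = 0.3 rows and recalculate the three effect sizes with the software that produced the table. Correcting the 490 alone would leave effect sizes that do not match the new number.

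If the normal approximation is kept for Table 4a, the values are 0.377, 0.361 and 0.298, and the change is six cells. If Table 4a is rerun with the t distribution, the values are 0.379, 0.362 and 0.299, and some R² = 0.2 cells also move: 0.353 becomes 0.354 and 0.279 becomes 0.280. Table 3a would need the same treatment to agree: 0.316 becomes 0.317 and 0.302 becomes 0.303. A one-line statement in section 6.2 of the method used would settle the choice. Design, enrolment and conduct do not change.
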